# 15. DATA / SAMPLE STORAGE FOR FUTURE USE

Clinical labs drawn as standard of care and as part of this study will be recorded in the subject's medical record and will be available to the subject. Since the non-clinical testing is being done strictly for research purposes, the results of these tests will not be recorded in the subject's medical record and subjects will not be informed of the results of these research assays.

Data and samples collected as part of this protocol will be used to perform the studies related to the primary, secondary and exploratory endpoints of this study. Any tissue that remains after these analyses have been performed will be deidentified and may be stored and used for future studies. These stored samples may also be shared with companies that are providing support for this study; this includes Incyte and their affiliates.

# 16. DATA AND SAFETY MONITORING PLAN

# 16.1 Data and Safety Monitoring

During the conduct of the study, the PI and his designee(s) will continually monitor the study to ensure that the study is conducted in compliance with the IRB-approved study protocol and that subject safety is maintained. Safety data will be reviewed by the PI or designee as soon as it is received. The review will include: the number of subjects consented/enrolled/completed, possible adverse events, and any other responses observed.

Version Date: 06Jun2023 Page 16 of 19

The FDA defines an adverse event (AE) as "any untoward medical occurrence associated with the use of a drug in humans, whether or not considered drug related" and a serious adverse event (SAE) as an AE that "results in any of the following outcomes: Death, a life-threatening adverse event, inpatient hospitalization or prolongation of existing hospitalization, a persistent or significant incapacity or substantial disruption of the ability to conduct normal life functions, or a congenital anomaly/birth defect" (Electronic Code of Federal Regulations, 13 Jan 2020).

The PI and study coordinator are the primary individuals charged with identification and reporting of all AE and SAE occurrences as well as protocol deviations. All SAEs that are considered serious, unexpected and related to the study participation will be reported to the IRB within 10 calendar days and all non-serious adverse events will be reported annually with the continuing review. The investigator will also notify the IRB of any serious deviations from the protocol, and any new information indicating added risk to subjects.

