# 5.2 Exclusion Criteria

# Individuals who meet any of these criteria are not eligible for enrollment as study participants:

- Unwillingness or inability to complete informed consent process or comply with the study protocol.
- Pregnant or breast-feeding women, or women planning to become pregnant or breastfeed during the study.
- History of coagulopathy, pulmonary embolism or deep venous thrombosis.
- History of cutaneous squamous cell carcinoma localized to the treatment area.
- Serum creatinine > 1.5 mg/dL, or alanine aminotransferase or aspartate aminotransferase  $> 1.5 \times$  upper limit of normal.
- Other dermatologic disease besides discoid lupus whose presence or treatments could complicate assessments.
- Other diseases besides dermatologic disorders whose treatment could complicate assessments. Subjects with systemic lupus erythematosus are permitted as long as they

Version Date: 06Jun2023 Page 6 of 19

- do not have unstable disease and meet all other criteria, including the exclusion criteria for systemic immunosuppressive or immunomodulating drugs (below).
- Topical treatments for discoid lupus within 2 weeks of Visit 2.
- Systemic immunosuppressive or immunomodulating drugs (e.g. oral or injectable corticosteroids, methotrexate, cyclosporine, mycophenolate mofetil, azathioprine) other than antimalarials (hydroxychloroquine, chloroquine, quinacrine) within 4 weeks or 5 half-lives of Visit 2 (whichever is longer).
- Potent systemic cytochrome P450 3A4 inhibitors or fluconazole within 2 weeks or 5 half-lives, whichever is longer, before Visit 2 (topical agents with limited systemic availability are permitted).
- Prior use of JAK inhibitors, systemic or topical, within the last 12 months.
- Ultraviolet (UV) therapy or tanning within 2 weeks prior to Visit 2 or during the duration of the treatment period.
- Any systemic or local infection that, in the opinion of the investigator, may compromise the safety of the subject or complicate assessments.
- Subjects allergic to lidocaine or with a history of keloids will not be allowed to provide an optional skin biopsy, but will be eligible for the remainder of the study.

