# 13. SUBJECT WITHDRAWALS

Subjects will be notified by the study coordinator and advised in the written informed consent provided that they have the right to withdraw from the study at any time without prejudice.

If participants of the study at any point meet the exclusion criteria established in this protocol, including pregnancy, study drug will be discontinued. In addition, study drug will be discontinued for any subject who experiences any of the following (per Common Terminology Criteria for Adverse Events v5.0):

- Grade 2 event in Cardiac Disorders
- Grade 3 event in any other System Organ Class

Current research does not suggest a treatment-associated increased risk for these events. Standard treatment will proceed as necessary to ensure optimal health for the subject. In this situation, long term data will no longer be collected, and only the data collected during the duration of participation of the clinical trial will be included in the data analysis and conclusions of the study.

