# 16.3 Reporting of Pregnancy to Incyte

An "Initial Pregnancy Report" or equivalent must be completed in full and emailed to [contact] or faxed to (+) [name] within 24 hours of discovery of a pregnancy of a subject who has taken the Incyte product or the pregnancy of a partner for a subject who has taken the Incyte product. The "Follow-up Pregnancy Report Form" or equivalent must be completed and emailed to [contact] or faxed to (+) [name] within 30 days after delivery, so that Incyte is provided with information regarding the outcome of the pregnancy. If the pregnancy results in any events which meet

Version Date: 06Jun2023 Page 17 of 19

the serious criteria (i.e., miscarriage or termination), the SAE reporting process needs to be followed and the timelines associated with a SAE should be followed.

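### The SAE definition in 16.1 has no limb for important medical events and does not match 16.3, so a DVT managed without admission, or a squamous cell carcinoma in the treated area, can stop study drug yet miss the 24-hour supplier report

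*Combined protocol and SAP*

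**What the plan says.** Section 16.1 defines an SAE as an adverse event with one of five outcomes. The first two are death and a threat to life. The third and fourth are "inpatient hospitalization or prolongation of existing hospitalization, a persistent or significant incapacity or substantial disruption of the ability to conduct normal life functions". The list closes with "or a congenital anomaly/birth defect". No other section adds to it, and 16.2 gives no definition of its own.

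Section 16.3, on pregnancy outcomes, refers to events that meet "the serious criteria (i.e., miscarriage or termination), the SAE reporting process needs to be followed", on SAE timelines.

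Section 13 stops study drug for anyone who comes to meet an exclusion criterion at any point. The criteria in Section 5.2 include "History of coagulopathy, pulmonary embolism or deep venous thrombosis" and "History of cutaneous squamous cell carcinoma localized to the treatment area". Section 13 also has separate grade-based stops, one of which is "Grade 2 event in Cardiac Disorders".

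Reporting depends on the classification:

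- **Supplier (16.2):** every SAE within 24 hours, whatever the investigator thinks of causality. Other adverse event information goes on a named form, with no deadline.
- **IRB (16.1):** events that are serious, unexpected and related within 10 calendar days; non-serious events annually. New information pointing to added risk must also be notified, with no deadline and no named events.

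**The concern.** The protocol marks out certain events as grave enough to bar entry and, under Section 13, to end treatment. One would expect such an event in a treated subject to reach the supplier quickly. The only fast supplier route opens when the event is classed as serious, and the 16.1 list can leave some of these events outside. Section 16.3 suggests that the authors had a broader notion of seriousness in mind but wrote it down only for pregnancy.

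More than this trial is at stake. Section 4.2 shows that the supplier holds an IND for the drug. Section 9.1 cites the supplier's brochure, which summarises 2350 exposed participants in terms of serious events. An event classed as non-serious here would not enter a summary of that kind as a serious one.

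**Working it through.** No calculation applies. The check sets the definition, the stopping rule and the reporting clocks side by side.

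**Step 1. Is the 16.1 list closed?** Yes. It names five outcomes and stops, with no residual category and no clause for investigator judgement.

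**Step 2. Do 16.1 and 16.3 agree?** No. An uncomplicated miscarriage or termination without admission fits none of the five outcomes on a plain reading, yet 16.3 calls it serious. The sections use different definitions. No report is lost for these two events, because 16.3 itself orders the SAE process.

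**Step 3. Which events can stop drug and still fall outside the list?**

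| Event | Stops drug under Section 13? | Serious under 16.1? |
|---|---|---|
| DVT, no admission, not judged life-threatening | Yes, if a new event creates the excluded history | Only if it meets the incapacity or disruption limb |
| Squamous cell carcinoma in the treatment area, managed without admission | Yes, on the same reading | Only if it meets that limb |
| DVT or PE that is life-threatening or leads to admission | Yes, on the same reading | Yes, already an SAE |

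The first two rows are the gap. The reading of a new event as creating a history is an interpretation, but it is what gives the at-any-point wording of Section 13 its effect.

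**Step 4. What happens to an event in the gap?**

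| Recipient | If classed as serious | If classed as non-serious |
|---|---|---|
| Supplier | 24 hours, any causality | Form specified, no deadline |
| IRB | 10 calendar days, if also unexpected and related | Annual review; untimed notice if judged new risk information |

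For the supplier, the difference is between a 24-hour limit and no limit. For the IRB, it is between 10 days, subject to two further tests, and the annual cycle, with a discretionary route alongside.

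**Step 5. Does another provision close the gap?** Section 13 attaches no reporting duty to discontinuation. Section 16.1 has the investigator or a designee review safety data on receipt, but that review sets no external deadline.

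**The case against.** Much of the case on the other side stands, and it limits the point.

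- A reader might infer that supplier reporting slips to the annual review. The text does not say so: the annual clause governs the IRB only, and 16.2 separately sends adverse event information to the supplier. The defect is a missing deadline, not an annual one.
- A reader might infer that enrolment would be over before the event came to light. The documents give no accrual rate or enrolment period, so this cannot be shown.
- The fourth limb covers significant as well as persistent incapacity, and substantial disruption of normal life. A symptomatic DVT could meet it. These events *can* be non-serious; they are not always so.
- A reader might infer that whatever stops drug should be an SAE, including every Grade 2 cardiac event. That does not follow. Discontinuation and seriousness are different thresholds: Section 13 also stops drug for meeting exclusions such as a raised creatinine or tanning.
- The exclusions are specific. They cover coagulopathy, DVT and PE, not thrombosis in general, and squamous cell carcinoma in the treatment area, not any new skin cancer.
- A new limb changes only whether an event is serious. The 10-day IRB report still needs it to be unexpected and related.
- Miscarriage and termination are already expedited by 16.3, so that mismatch is one of drafting.

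Section 16.1 presents its definition as a quotation from a regulation. Whether it is complete cannot be checked from the documents, and the point does not depend on it. After all these limits, two things remain: the list has no place for an important event outside its five outcomes, and nothing else in the protocol puts a deadline on telling the supplier about one.

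**Conclusion.** The point holds in this limited form. Section 16.1 is a closed list that differs from 16.3. Followed as written, it allows a DVT managed without admission, or a squamous cell carcinoma in the treatment area, to end treatment without triggering the 24-hour supplier report.

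The conclusion rests on two assumptions: that a new event counts as the excluded history for Section 13, and that the particular event does not meet the incapacity or disruption limb.

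The effect is on the timing of safety reports; the efficacy analysis is untouched. Its frequency cannot be estimated, because the documents give no event rates. With 15 subjects treated for 12 weeks, and with Section 13 saying that current research does not suggest a raised risk of the events behind its grade-based stops, few such events are likely. It should still be corrected, since each one would be of interest to the supplier's wider safety record.

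**What to change.** In 16.1, add a sixth limb to the definition, for example: *or an important medical event that, in the investigator's judgement, may jeopardise the subject or need intervention to prevent one of the outcomes above*. Give new DVT or PE, and squamous cell carcinoma in the treatment area, as examples. Have 16.1, 16.2 and 16.3 all refer to this one definition, so that the reference to serious criteria in 16.3 points to text that exists. If the sponsor prefers to keep miscarriage and termination as events named for SAE handling, 16.1 can name them by cross-reference to 16.3.

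The change concerns reporting only and leaves the stopping rules in Section 13 as they are. It needs one sentence in 16.1 and cross-references in 16.2 and 16.3. The running cost is at most a few extra expedited reports in 15 subjects.

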# **16.2 SAE Reporting to Incyte**

The Principal Investigator (PI) must report all Serious Adverse Events (SAEs) to Incyte within 24 hours of learning of an event, regardless of the PI's causality assessment. This notification should be provided on a completed Serious Adverse Event (SAE) form. SAE reporting for each subject begins the day the informed consent is signed by the patient and within 30 days after subject has completed or discontinued from the study or has taken last dose of the study drug, or as described in the protocol.

SAEs, occurring using Incyte study drug, are reported in accordance with the effective protocol. SAEs occurring with any other commercial drug are reported to the manufacturer of that drug in accordance with regulations and protocol.

Initial SAEs and/or subsequent follow-up reports should be reported via email to [contact] or fax (+) [name]. SAE reports should be for a single subject. SAE forms should be sent with a cover sheet and any additional attachments.

All adverse event information is reported to Incyte on the Principal Investigator's/Institution's Adverse Event Report Form, or a CIOMS-I or MedWatch Form FDA 3500A, or on an Adverse Event Report Form which may be provided by Incyte upon request. The Principal Investigator does not provide medical records (e.g., discharge summary) to Incyte, unless specifically requested.

# 16.3 Reporting of Pregnancy to Incyte

An "Initial Pregnancy Report" or equivalent must be completed in full and emailed to [contact] or faxed to (+) [name] within 24 hours of discovery of a pregnancy of a subject who has taken the Incyte product or the pregnancy of a partner for a subject who has taken the Incyte product. The "Follow-up Pregnancy Report Form" or equivalent must be completed and emailed to [contact] or faxed to (+) [name] within 30 days after delivery, so that Incyte is provided with information regarding the outcome of the pregnancy. If the pregnancy results in any events which meet

Version Date: 06Jun2023 Page 17 of 19

the serious criteria (i.e., miscarriage or termination), the SAE reporting process needs to be followed and the timelines associated with a SAE should be followed.

# 17. DATA ANALYSIS PLAN

This exploratory study has a sample size of 15 subjects. Given the small sample size, a robust statistical analysis will be limited. The primary endpoint will be a  $\geq$  2-point reduction in IGA score. The mean percentage change from baseline will be assessed for the secondary endpoints (CLASI, CLASI-A, CLASI-D, NRS, EI, MI). Statistical analysis of exploratory endpoints comparing skin tissue before and after ruxolitinib treatment will be performed in accordance with the technique being used (histology, flow cytometry, RNAseq). Analyses of DLE histology (H&E, IHC, IFM) will include common histologic features (follicular plugging, interface change, etc.), cell counts of the immune infiltrate, and markers of IFN response. Flow cytometric analysis will evaluate the immune infiltrate, including T and B cell subsets. The focus of the RNAseq analysis will be on interferon expression, though other analyses may be performed. Differences will be considered significant at p < 0.05.

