# 4. STUDY DESIGN

This is a 12-week, single-center, open-label study of ruxolitinib 1.5% cream for the treatment of discoid lupus. The primary endpoint is a ≥ 2-point reduction in Investigator's Global Assessment (IGA) score at Week 12 compared to baseline. Secondary endpoints at Week 12 include the mean percentage change from baseline in the Cutaneous Lupus Erythematosus Disease Area and Severity Index (CLASI), CLASI-A (activity) and CLASI-D (damage) scores; the change in erythema and pigmentation as determined by quantitative photographic analysis; and the change in numeric rating scale (NRS) for pain and pruritus. Exploratory endpoints of skin biopsies will evaluate cellular and molecular features of discoid lesions preand post-treatment for 1) predictors of treatment response, and 2) treatment response to ruxolitinib. Quantitative and qualitative measures of the cutaneous inflammatory response, including evaluation of the immune cell infiltrate and IFN signature, will be assessed.

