# 4.1. SUBJECT POPULATION

# 4.1.1 Number of Subjects

Fifteen subjects will be consented to enroll in this study. This small sample size is justified by the rarity of this condition and the exploratory nature of the study.

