# 5. INCLUSION AND EXCLUSION CRITERIA

#### 5.1 Inclusion Criteria

# Individuals who meet all of the following criteria are eligible for enrollment as study participants:

- Ability to understand and comply with the protocol and provide informed consent.
- Speaks English.
- Age  $\geq$  18 years.
- Clinical diagnosis of discoid lupus as assessed by the PI.
- At least one active (inflamed) discoid lesion with an IGA score of  $\geq 3$  and with a diameter  $\geq 1$  cm at screening and baseline. Two lesions with equal scores will be necessary if consenting to pre-and post-treatment biopsies.
- Maximum body surface area of 20%.

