## 7. CONSENT PROCESS

### 7.1 Process of Consent

The consent process will provide information about the study to a prospective participant and will allow adequate time for review and discussion prior to his/her decision. The PI or a qualified study member listed in the CLICK IRB protocol will review the consent form with the participant and answer questions. Consent designees will be listed on the site delegation of responsibilities log, complete consenting certification, and have knowledge of the protocol and study procedures. The PI or designee will meet directly with subjects in a private room and the consent form will be read in its entirety. Any questions will be answered to the subject's satisfaction. The subject's capacity to comprehend the information in the consent form will be assessed by asking questions about the content and encouraging the subject to describe briefly the study procedures. Subjects will be assured that enrollment is voluntary and that they are free to not participate or to withdraw at any time, without risking loss of present or future care that they would otherwise receive. It will be explained to the subject that those who consent to participate in this study will have their contact information and medical history stored in the database. Subjects will be informed that if they withdraw consent, no new information will be collected, and they can choose to have any stored samples discarded. However, data generated from previously used samples may be retained. Subjects will be allowed as much time as necessary to provide consent. Subjects will provide consent by signing the informed consent form for this study. Subjects will receive a signed copy of the consent form. The consent process will be ongoing. The consent form will be revised, and the subjects re-consented, when important new safety information is available, the protocol is amended, and/or new information becomes available that may affect participation in the study.

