#### 8. STUDY PROCEDURES

Version Date: 06Jun2023 Page 8 of 19

This study will be a single-arm trial of ruxolitinib 1.5% cream applied twice daily for 12 weeks. Only active lesions will be treated, defined as those with erythema, scale, pain, or pruritus. Each subject will be provided with ruxolitinib cream.

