### 8.2.1 Clinical Assessments

Clinical Assessments: A detailed physical exam, past medical history and vital signs will be performed at study visit 1. A problem-focused physical exam, interval history and vital signs (heart rate, blood pressure, temperature, weight) will be performed at visits 2-7. Adverse events will be assessed at study visits 2-7.

IGA: The Investigator's Global Assessment will be performed at study visits 2-6. The IGA is an instrument to rate the severity of the subject's global disease. This IGA is comprised of a 5-point scale of disease activity ranging from 0 to 4 as follows:

- 0: "clear," no erythema or scale
- 1: "almost clear," pink erythema without scale
- 2: "mild," pink erythema with scale
- 3: "moderate," red erythema with scale
- 4: "severe," purple/violaceous or hemorrhagic/crusted erythema OR hypertrophic/ verrucous scale

CLASI: The Cutaneous Lupus Area and Severity Index will be performed at study visits 2-6. This is a validated measurement instrument designed for use in clinical trials to assess disease activity and damage in subjects with cutaneous lupus. The CLASI is comprised of two parts, CLASI-A that measures disease activity (erythema and scale), and CLASI-D that measures disease damage (pigmentation and scarring).

NRS: Subjects will maintain a symptom diary every day for 12 weeks. Specifically, subjects will rate pain and itch separately using a numeric rating scale (NRS) and the questions below. Symptom diaries will be reviewed at study visits 2-6.

On a scale of no itch (0) to worst imaginable itch (10), how itchy was the worst discoid

Version Date: 06Jun2023 Page 9 of 19

lupus lesion in the last 24 hours?

On a scale of no pain (0) to worst imaginable pain (10), how painful was the worst discoid lupus lesion in the last 24 hours?

Photography: Photographs of all discoid lesions will be taken at study visits 2-6. The Haiku app or Canto app will be used to directly load photos into the secure Epic medical record system. Images will be extracted from Epic, and analyzed as described. In brief, a melanin index (MI) and an erythema index (EI) will be generated for each lesion using Image J software analysis. The analysis uses perilesional skin to normalize the photograph. Images from serial visits will then be compared, as well as between treatment groups.

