# 8.2.5 Data Analysis

**Primary Endpoint:**  $A \ge 2$ -point reduction in IGA score at Week 12 compared to baseline.

*Secondary Endpoints*: The mean percentage change at Week 12 from baseline in CLASI, CLASI-A and CLASI-D scores; erythema (EI) and melanin indices (MI); and NRS for pain and pruritus.

Version Date: 06Jun2023 Page 12 of 19

*Exploratory Endpoints*: The change in inflammatory response, which includes the degree of inflammation, composition of inflammatory infiltrate, and interferon (IFN) signature.

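### NRS pain and itch are to be summarised as mean percentage change, but a subject may start at 0, and the plan neither says how the percentage is formed nor what to do with zeros

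*Combined protocol and SAP*

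**What the plan says.** Three sections define the secondary measures, and they do not match for the NRS.

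- Section 17 (Data Analysis Plan): "The mean percentage change from baseline will be assessed for the secondary endpoints (CLASI, CLASI-A, CLASI-D, NRS, EI, MI").
- Section 8.2.5 (Data Analysis) uses the same measure, with both symptom scores at the end of its list: "mean percentage change at Week 12 from baseline in CLASI, CLASI-A and CLASI-D scores; erythema (EI) and melanin indices (MI); and NRS".
- Section 4 (Study Design) gives percentage change for CLASI, CLASI-A and CLASI-D, but for the NRS says only "and the change in numeric rating scale (NRS) for pain and pruritus".

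Section 8.2.1 anchors the itch question at zero ("On a scale of no itch (0) to worst imaginable itch (10") and words the pain question in the same way. Section 5.1 requires "At least one active (inflamed) discoid lesion with an IGA score of" 3 or more and a diameter of at least 1 cm. In Section 8.2.1 the IGA grades are described by erythema and scale. Section 8 lists symptoms as only one of several ways for a lesion to count as active: "Only active lesions will be treated, defined as those with erythema, scale, pain, or pruritus". Section 5.2 does not exclude subjects without symptoms. No section says how a baseline of 0 is to be handled, or whether the percentage is formed per subject or on group means.

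**The concern.** A subject with a red, scaly lesion that neither hurts nor itches is eligible and would record 0 on one or both scales at baseline. Dividing by that baseline is impossible. A subject who starts at 1 can improve by at most 100% but can worsen by up to 900%, so a single such subject can move the mean of a very small sample.

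Two analysts who both follow the text could therefore report different NRS results from the same data, depending on what they do with zeros and which kind of percentage they compute. The study is open label, so without a rule the choice would be made by people who have seen the data. Leaving zeros out is also not neutral. Those subjects cannot improve; they can only stay at 0 or get worse, and Section 9.1 lists pain and itch among the effects observed with the cream.

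**Working it through.** The plan gives no figure on this point, so there is nothing to reproduce. The check has four steps.

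**Inputs.** From the documents: both NRS scales run from 0 to 10 (Section 8.2.1), and "Fifteen subjects will be consented to enroll in this study" (Section 4.1.1). Fifteen is a ceiling, because eligibility is confirmed at Visit 2, after consent (Section 8.2.4), and study drug can be discontinued (Section 13). Assumed, because the documents give no baseline distribution: the share *q* starting at 0, and every score used below.

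**Step 1. Definition.** Per-subject percentage change = 100 × (Week 12 − baseline) / baseline. At baseline 0 it is undefined. A one-point change equals 100% at baseline 1, 50% at baseline 2, 20% at baseline 5 and 10% at baseline 10.

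**Step 2. Chance of at least one undefined value** on one scale, 1 − (1 − *q*)^n:

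| Evaluable n | q = 10% | q = 20% | q = 30% |
|---|---|---|---|
| 15 | 79.4% | 96.5% | 99.5% |
| 12 | 71.8% | 93.1% | 98.6% |
| 10 | 65.1% | 89.3% | 97.2% |

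**Step 3. Zeros left out.** Suppose 12 subjects go from 6 to 3, and 3 start at 0 and end at *w*. The per-subject mean uses only the 12 and is −50% whatever *w* is. For all 15, the baseline mean is (12 × 6)/15 = 4.8 and the Week 12 mean is (36 + 3*w*)/15:

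| w | Group means | Change of group mean | Absolute change |
|---|---|---|---|
| 0 | 4.8 to 2.4 | −50.0% | −2.4 |
| 1 | 4.8 to 2.6 | −45.8% | −2.2 |
| 2 | 4.8 to 2.8 | −41.7% | −2.0 |

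On the group-mean scale the direction is general. Subjects at 0 add nothing to the baseline total, and they add either nothing or a positive amount at Week 12. Removing them therefore leaves the percentage as it was or makes it look better.

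**Step 4. Low baselines.** Now let some subjects start at 1 and end at *w*, with the rest going from 6 to 3.

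- Three of 15: per-subject mean = (12 × (−50) + 3 × 100(*w* − 1))/15; group mean from 5.0 to (36 + 3*w*)/15.
- One of 15: per-subject mean = (14 × (−50) + 100(*w* − 1))/15; group mean from 85/15 = 5.67 to (42 + *w*)/15.

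| w | Three: per subject | Three: group mean | One: per subject | One: group mean |
|---|---|---|---|---|
| 0 | −60% | −52% | −53.3% | −50.6% |
| 1 | −40% | −48% | −46.7% | −49.4% |
| 2 | −20% | −44% | −40.0% | −48.2% |
| 3 | 0% | −40% | −33.3% | −47.1% |

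The two readings can differ in either direction, so the net direction over zeros and low baselines together is unknown.

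**The case against.** The strongest reply is that the plan never says the percentage is per subject. If it means the percentage change of the group mean, a few zeros do no harm. That is correct, and it limits the point: the value is undefined only under the per-subject reading. It does not remove the point, because the plan does not choose between readings that give different numbers.

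Size is also fairly challenged. Every share and score above is assumed. The diary asks about the worst lesion, which makes a 0 less likely than an average over lesions would. The documents also do not say which diary entries form the baseline. In the zeros-left-out example the gap is 0 to 8 percentage points, and the larger low-baseline gaps need subjects who worsen. Section 17 itself concedes that the sample limits the statistical analysis.

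A reader might infer three stronger things that the documents do not support.

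- *New pain or itch would be lost.* It would not. Adverse events are assessed at visits 2 to 7 and diaries reviewed at visits 2 to 6 (Sections 8.2.1 and 8.2.4), and irritation of the surrounding skin is part of the focused exam (Section 8.2.2). Only the NRS efficacy summary could miss it.
- *CLASI-D has the same defect and should change measure.* It scores pigmentation and scarring, and no entry criterion requires either, so a zero is possible. But this is an inference, since the scoring range is not printed. All three sections agree on percentage change for CLASI-D, and changing only Sections 8.2.5 and 17 would create a conflict with Section 4.
- *CLASI, CLASI-A, EI and MI are safe.* An IGA of 3 or more makes a zero activity score implausible but does not rule out a low one. No formula for EI or MI is printed. The documents settle neither question.

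**Conclusion.** The point holds for NRS pain and NRS itch. Sections 8.2.5 and 17 prescribe a measure that cannot be computed per subject for some eligible subjects, is unstable for others, and is ambiguous between two calculations; Section 4 words it differently. Leaving out subjects at 0 makes the NRS efficacy summary either unchanged or too favourable.

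How often this would occur rests on an assumed share at 0. With 10% to 30%, at least one undefined value is likely at any plausible sample size here (65% to 99.5%). If nobody starts at 0, only the low-baseline instability and the ambiguity remain.

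The reach is modest: two secondary measures of an exploratory single-arm study, with the primary IGA endpoint untouched. It should still be fixed before analysis, because the remedy needs no new data and agrees with wording already in Section 4.

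**What to change.** In Sections 8.2.5 and 17:

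1. Analyse NRS pain and NRS itch as absolute change from baseline to Week 12 in all subjects with both values, in line with Section 4, and report how many had a baseline of 0. If a percentage is wanted, give 100 × (mean Week 12 / mean baseline − 1) in the same subjects.
2. Keep percentage change for CLASI-D, but report absolute change alongside it and the number with a baseline of 0.
3. Reconcile the wording for erythema and pigmentation, where Section 4 says change and Sections 8.2.5 and 17 say percentage change.

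One sentence in Section 8.2.1 naming the diary entries that form the baseline and Week 12 NRS values would make the count at 0 reproducible.

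**Cost.** Wording only, with no new data, visits or procedures. Section 7.1 provides for re-consent on amendment ("the subjects re-consented, when important new safety information is available, the protocol is amended"), so that step applies as written. The NRS loses a per-subject relative scale, and subjects who stay at 0 shrink the absolute mean. With 3 of 15 staying at 0 and 12 going from 6 to 3, it is (12 × (−3))/15 = −2.4 points overall, against −3.0 in those with symptoms. That is why the number at 0 should be shown beside the result.
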